12.5.1 Anti-Cancer Activity Analyses

The All Treated Population will be used for anti-cancer activity analyses. Since this is a Phase I study, anti-cancer activity will be evaluated by investigator assessment based on clinical evidence and response criteria provided in Appendix 3 through Appendix 7. If data warrant, the response data will be summarized by disease cohort and by dose level. Anti-cancer activity analyses will also be performed based on Response-Evaluable population as sensitivity analysis.

In a supportive analysis, for LGG and NF-1 patients, anti-cancer activity will also be evaluated by independent review assessment based on clinical evidence and response criteria provided in Appendix 5 and 6 respectively.

Correlation analysis will be conducted to explore any relationship between the subject's PK or PD evaluations and tumor response based on disease specific response criteria provided in [Appendix 3](#) through [Appendix 7](#).

Full details will be specified in the SAP.

12.5.2 Safety Analyses

The Safety Population will be used for the analysis of safety data. All serially collected safety endpoints (e.g., laboratory tests, vital signs, ECGs) will be summarized according to the scheduled, nominal visit at which they were collected and across all on-treatment time points

using a “worst-case” analysis. Complete details of the safety analyses will be provided in the SAP.

12.5.2.1 Extent of Exposure

The number of subjects administered study treatment will be summarized according to the duration of therapy. Further details will be provided in the SAP.

12.5.2.2 Adverse Events

Adverse events (AEs) will be coded using the standard MedDRA and grouped by system organ class. Adverse events (AEs) will be graded by the investigator according to the NCI-CTCAE v4.03 (NCI 2009).

Events will be summarized by frequency and proportion of total subjects, by system organ class and preferred term. Separate summaries will be given for all AEs, treatment-related AEs, SAEs and AEs leading to discontinuation of study treatment. AEs, if listed in the NCI-CTCAE v4.03 (NCI 2009) will be summarized by the maximum grade. Otherwise, the AEs will be summarized by maximum intensity.

Characteristics (e.g., number of occurrences, action taken, grade, etc) of the following AEs of special interest will be summarized separately: rash, diarrhea.

The incidence of deaths and the primary cause of death will be summarized.

Dose-limiting toxicities (DLTs) will be listed for each subject and summarized by dose cohort according to Novartis standards. Further details will be provided in the SAP.

12.5.2.3 Clinical Laboratory Evaluations

Hematology, clinical chemistry and urinalysis data will be summarized using frequencies and proportions according to NCI-CTCAE v4.03 (NCI 2009) For laboratory tests where grades are not defined by CTCAE v4.03, results will be categorized as low/normal/high based on laboratory normal ranges and will be summarized using proportions. Further details will be provided in the SAP.

12.5.2.4 Other Safety Measures

Data for vital signs, ECGs, and ECHOs will be summarized based on predetermined criteria identified to be of potential clinical interest. Further details will be provided in the SAP.

12.5.3 Pharmacokinetic Analyses

PK parameters for study treatment (trametinib, dabrafenib and its metabolites) for subjects in whom the full blood sampling scheme will be used will be calculated with standard non-compartmental methods. The PK parameters calculated with non-compartmental methods include; AUC(0-t), C_{max}, T_{max}, C_τ, CL/F, and AUC(0-τ) (where τ = 24 hr for trametinib and 12 hr for dabrafenib). For subjects in whom the sparse blood sample collection scheme will be used, AUC(0-τ) and the average steady-state concentration will be estimated with a population

PK model. Final PK parameters will be summarized and will be compared to historical adult data.

All trametinib and dabrafenib concentration-time data may be combined and included in a population PK analysis that will examine the influence of demographics (especially age and weight) on the PK of study treatment. Trametinib and dabrafenib PK parameters estimated in the population PK analysis will include: apparent clearance following oral dosing (CL/F), central volume of distribution (Vc/F), and absorption rate constants (ka) (trametinib only). Sparse PK data collected for each treatment may be pooled with the rest of the PK data collected for this treatment from all parts of this study and in addition to adult data.

PK analysis will be under the supervision of Novartis. The assay for trametinib, dabrafenib and its metabolites are conducted under GLP conditions and are validated for determination of the PK primary endpoint.

12.5.3.1 Pharmacokinetic Parameters

PK analysis of drug concentration-time data will be conducted by non-compartmental methods under the direction of Novartis. The following PK parameters will be determined if data permit:

- maximum observed plasma concentration (C_{max}).
- time to C_{max} (t_{max}).
- area under the plasma concentration-time curve (AUC(0-t), AUC(0-τ) (repeat dosing)).
- oral clearance (CL/F).
- C_τ at steady state

Population PK parameters may include the following and are dependent upon the final population PK model for both trametinib and/or dabrafenib: apparent clearance following oral dosing (CL/F), central volume of distribution (Vc/F), absorption rate constants (ka) and MTIME (time when absorption rate changes).

12.5.3.2 Statistical Analysis of Pharmacokinetic Data

Statistical analyses of the PK parameters data will be the responsibility of Novartis with actual analyses being performed by Novartis and/or a designated CRO.

Drug concentration-time data will be listed for each subject and summarized by descriptive statistics at each time point by cohort and by study treatment.

12.5.3.3 Translational Research Analyses

The results of translational research investigations will be reported separately from the main clinical study report (CSR). All endpoints of interest from all comparisons will be descriptively and/or graphically summarized as appropriate to the data.

Further details on the translational research analyses will be addressed in the SAP.

13 Study Conduct Considerations

13.1 Posting of Information on Clinicaltrials.gov

Study information from this protocol will be posted on clinicaltrials.gov before enrollment of subjects begins.

13.2 Regulatory and Ethical Considerations, Including the Informed Consent Process

Prior to initiation of a study site, Novartis will obtain approval from the appropriate regulatory agency to conduct the study in accordance with International Conference on Harmonization Good Clinical Practice (ICH GCP) and applicable country-specific regulatory requirements.

The study will be conducted in accordance with all applicable regulatory requirements.

The study will be conducted in accordance with ICH GCP, all applicable subject privacy requirements, and the ethical principles that are outlined in the Declaration of Helsinki 2008, including, but not limited to:

- IRB/IEC review and approval of study protocol and any subsequent amendments.
- Subject informed consent/assent.
- Investigator reporting requirements.

Novartis will provide full details of the above procedures, either verbally, in writing, or both.

Written informed consent and assent when applicable must be obtained from each subject or their legally authorized representative prior to participation in the study.

13.3 Urgent Safety Measures

If an event occurs that is related to the conduct of the study or the development of the IP, and this new event is likely to affect the study of subjects, the Sponsor, and the investigator will take appropriate urgent safety measures to protect subjects against any immediate hazard.

The Sponsor will work with the investigator to ensure the IRB/IEC is notified.

13.4 Quality Control (Study Monitoring)

In accordance with applicable regulations, Good Clinical Practice (GCP) and Novartis personnel (or designated Clinical Research Organization [CRO]) will contact the site prior to the start of the study to review with the site staff the protocol, study requirements, and their responsibilities to satisfy regulatory, ethical, and Novartis requirements. When reviewing data collection procedures, the discussion will include identification, agreement and documentation of data items for which the eCRF will serve as the source document.

The investigator and the head of the medical institution (where applicable) agrees to allow the monitor direct access to all relevant documents and to allocate their time and the time to their staff to monitor to discuss findings and any issues.

Novartis (or designated CRO) personnel will monitor the study to ensure that the:

- Data are authentic, accurate, and complete.
- Safety and rights of subjects are being protected.
- Study is conducted in accordance with the currently approved protocol and any other study agreements, ICH GCP, and all applicable regulatory requirements.

13.5 Quality Assurance

To ensure compliance with ICH GCP and all applicable regulatory requirements, Novartis may conduct quality assurance audits of the site. Regulatory agencies may conduct a regulatory inspection at any time during or after completion of the study. In the event of an audit or inspection, the investigator (and institution) must agree to grant the auditor(s) and inspector(s) direct access to all relevant documents and to allocate their time and the time of their staff to discuss any findings/relevant issues.

13.6 Study and Site Closure

The end of the study will be defined as the date of the last visit of the last subject enrolled.

Upon completion or termination of the study, Novartis personnel (or designated CRO) will conduct site closure activities with the investigator or site staff (as appropriate), in accordance with applicable regulations, ICH GCP, and Novartis Standard Operating Procedures.

Novartis reserves the right to temporarily suspend or terminate a study cohort or the entire study at any time for reasons including (but not limited to) safety issues, ethical issues, or severe noncompliance. If Novartis determines that such action is required, Novartis will discuss the reasons for taking such action with the investigator or head of the medical institution (where applicable). When feasible, Novartis will provide advance notice to the investigator or head of the medical institution of the impending action.

If a study is suspended or terminated for safety reasons, Novartis will promptly inform all investigators, heads of the medical institutions (where applicable), and/or institutions conducting the study. Novartis will also promptly inform the relevant regulatory authorities of the suspension/termination along with the reasons for such action. Where required by applicable regulations, the investigator or head of the medical institution must inform the IRB/IEC promptly and provide the reason(s) for the suspension/termination.

Novartis may also close study sites which fail to recruit subjects within a predefined timeframe.

13.7 Records Retention

Following closure of the study, the investigator or head of the medical institution (where applicable) must maintain all site study records (except for those required by local regulations to be maintained elsewhere) in a safe and secure location. The records must be easily accessible when needed (e.g., for a Novartis audit or regulatory inspection) and must be available for review in conjunction with assessment of the facility, supporting systems, and relevant site staff.

Where permitted by local laws/regulations or institutional policy, some or all of the records may be maintained in a format other than hard copy (e.g., microfiche, scanned, electronic); however, caution must be exercised before such action is taken. The investigator must ensure that all reproductions are legible and are a true and accurate copy of the original. In addition, they must

meet accessibility and retrieval standards, including regeneration of a hard copy, if required. The investigator must also ensure that an acceptable back-up of the reproductions exists and that there is an acceptable quality control procedure in place for creating the reproductions.

Essential documents (written and electronic) should be retained for a period of not less than fifteen (15) years from the completion of the Clinical Trial unless the Sponsor provides written permission to dispose of them or, requires their retention for an additional period of time because of applicable laws, regulations and/or guidelines.

The investigator must notify Novartis of any changes in the archival arrangements, including, but not limited to archival of records at an off-site facility or transfer of ownership of the records in the event that the investigator is no longer associated with the site.

13.8 Provision of Study Results to Investigators, Posting of Information on Publicly Available Clinical Trials Registers and Publication

Where required by applicable regulatory requirements, an investigator signatory will be identified for the approval of the clinical study report. The investigator will be provided reasonable access to statistical tables, figures, and relevant reports and will have the opportunity to review the complete study results at a Novartis site or other mutually-agreeable location.

Novartis will also provide the investigator with the full summary of the study results. The investigator is encouraged to share the summary results with the study subjects, as appropriate.

15.1 Appendix 1: Karnofsky and Lansky Performance Scores

PERFORMANCE STATUS CRITERIA			
Karnofsky and Lansky performance scores are intended to be in multiples of 10			
Karnofsky (age ≥16 years of age)		Lansky (age <16 years)	
Score	Description	Score	Description
100	Normal, no complaints no evidence of disease.	100	Fully active, normal.
90	Able to carry on normal activity, minor signs of symptoms of disease.	90	Minor restrictions in physically strenuous activity.
80	Normal activity with effort, some signs of symptoms of disease.	80	Active, but tires quickly.
70	Cares for self, unable to carry on normal activity or do active work.	70	Both greater restriction of and less time spent in play activity.
60	Requires occasional assistance, but is able to care for most of his/her needs.	60	Up and around, but minimal active play, keeps busy with quieter activities.
50	Requires considerable assistance and frequent medical care.	50	Gets dressed, but lies around much of the day; no active play, able to participate in all quiet play and activities.
40	Disabled, requires special care and assistance.	40	Mostly in bed, participates in quiet activities.
30	Severely disabled, hospitalization indicated. Death not imminent.	30	In bed, needs assistance even for quiet play.
20	Very sick, hospitalization indicated. Death not imminent.	20	Often sleeping; play entirely limited to very passive activities.
10	Moribund, fatal processes progressing rapidly.	10	No play, does not get out of bed.

Reference

15.2 Appendix 2: Dosing Nomograms

Dosing nomograms - Trametinib

DOSE LEVEL: 0.0125 mg/kg/dose SUBJECT WEIGHT: ≤ 19.4 kg FORMULATION: TRAMETINIB 0.05 MG/ML ORAL SOLUTION [At this dose level, the 0.05 mg/mL oral solution will be administered to all patients ≤19.4 kg]				
Actual weight* (kg)	Dose	Dose	Dose Reduction	
	mL	mg	mL	mg
2.5 – 3	0.6	0.03	0.4	0.02
3.1-3.6	0.8	0.04	0.6	0.03
3.7-4.3	1	0.05	0.8	0.04
4.4-5.2	1.2	0.06	0.9	0.45
5.3-6.1	1.4	0.07	1.1	0.55
6.2-6.7	1.6	0.08	1.2	0.06
6.8-7.6	1.8	0.09	1.4	0.07
7.7-8.6	2	0.1	1.5	0.075
8.7-9.3	2.2	0.11	1.7	0.085
9.4-10.1	2.4	0.12	1.8	0.09
10.2-10.7	2.6	0.13	2	0.1
10.8-11.3	2.8	0.14	2.1	0.105
11.4-12.2	3	0.15	2.3	0.115
12.3-12.9	3.2	0.16	2.4	0.12
13-13.8	3.4	0.17	2.6	0.13
13.9-14.6	3.6	0.18	2.7	0.135
14.7-15.5	3.8	0.19	2.9	0.145
15.6-16.5	4	0.2	3	0.15
16.6-17.4	4.2	0.21	3.2	0.16
17.5-18	4.4	0.22	3.3	0.165
18.1-18.7	4.6	0.23	3.5	0.175
18.8-19.4	4.8	0.24	3.6	0.18

*weight measured within 7 days of the start of the cycle.

Actual weight* (kg)	Dose		Dose Reduction	
	mL	mg	mL	mg
19.5- 23.5	5	0.25	3.8	0.19
23.6- 28.5	6	0.3	4	0.2
28.6-34	7.5	0.375	6	0.3
34.1-38	9	0.45	6.8	0.34
38.1-45	10	0.5	7.5	0.375
45.1-55	12.5	0.625	10	0.5
55.1-67	15	0.75	12	0.6
67.1-72	17	0.85	12.5	0.625
≥72.1	20	1.0	15	0.75

*weight measured within 7 days of the start of the cycle

Actual weight* (kg)	Dose		Dose Reduction	
	mL	mg	mL	mg
2-2.5	1	0.05	0.7	0.035
2.6-3.5	1.4	0.07	1.1	0.055
3.6-4.5	2	0.1	1.5	0.075
4.6-5.7	2.5	0.125	2	0.1
5.8-6.9	3	0.15	2.3	0.115
7-9.9	4	0.2	3	0.15

*weight measured within 7 days of the start of the cycle

Actual weight* (kg)	Dose		Dose Reduction	
	mL	mg	mL	mg
10-12.5	5	0.25	3.8	0.19
12.6-16.5	7.5	0.375	5	0.25
16.6- 24.5	10	0.5	7.5	0.375
24.6- 35	15	0.75	10	0.5
35.1-45	20	1.0	15.0	0.75
45.1- 55	25	1.25	17.5	0.875
55.1- 68	30	1.5	22.5	1.125
68.1- 72	35	1.75	25	1.25
> 72	40	2	30	1.5

*weight measured within 7 days of the start of the cycle

	DOSE LEVEL: 0.04 mg/kg/dose SUBJECT WEIGHT: < 10 kg FORMULATION: TRAMETINIB 0.05 MG/ML ORAL SOLUTION [At this dose level, the 0.05 mg/mL oral solution will be administered to all patients ≤9.9 kg]			
Actual weight* (kg)	Dose		Dose Reduction	
	mL	mg	mL	mg
2-2.5	1.8	0.09	1.2	0.06
2.6-3.5	2	0.1	1.6	0.08
3.6-4.5	3.2	0.16	2.4	0.12
4.6-5.8	4	0.2	3	0.15
5.9-7.5	5	0.25	3.6	0.18
7.6-9.9	7.5	0.375	5	0.25

*weight measured within 7 days of the start of the cycle

Actual weight* (kg)	Dose		Dose Reduction	
	mL	mg	mL	mg
10-14	10	0.5	7.5	0.375
14.1-17	12.5	0.625	9.5	0.475
17.1- 23.5	15	0.75	10	0.5
23.6- 30	20	1.0	15	0.75
30.1-35	25	1.25	17.5	0.875
35.1- 45	30	1.5	20	1.0
45.1- 60	40	2	30	1.5
60.1- 69.9	40	2	30	1.5
≥70	40	2	30	1.5

*weight measured within 7 days of the start of the cycle

	DOSE LEVEL: 0.032 mg/kg/dose SUBJECT WEIGHT: < 15 kg FORMULATION: TRAMETINIB 0.05 MG/ML ORAL SOLUTION [At this dose level, the 0.05 mg/mL oral solution will be administered to all patients ≤14.9 kg]		
Actual weight* (kg)	Dose		Dose Reduction
	mL	mg	
2-2.4	1.4	0.07	Please refer to 0.025 mg/kg dosing nomogram ('Dose' column)
2.5-3	1.8	0.09	
3.1-3.7	2.2	0.11	
3.8-4.5	2.7	0.13	
4.6-5.5	3.2	0.16	
5.6-6.7	3.9	0.20	
6.8-8.1	4.8	0.24	
8.2-9.8	5.8	0.29	
9.9-11.9	7.0	0.35	
12-13.9	8.3	0.41	
14-14.9	9.2	0.46	

*weight measured within 7 days of the start of the cycle

	DOSE LEVEL: 0.032 mg/kg/dose SUBJECT WEIGHT: ≥ 15 kg FORMULATION: TRAMETINIB 0.05 MG/ML ORAL SOLUTION		
Actual weight* (kg)	Dose		Dose Reduction
	mL	mg	
15-17.9	10.5	0.53	Please refer to 0.025 mg/kg dosing nomogram ('Dose' column)
18-21.5	12.6	0.63	
21.6-25.9	15.2	0.76	
26-31.2	18.3	0.92	
31.3-37.5	22.0	1.10	
37.6-45.1	26.5	1.32	
45.2-54.3	31.8	1.59	
54.4-60	36.6	1.83	
>60	40.0	2	

*weight measured within 7 days of the start of the cycle

Dose and treatment schedule for trametinib tablets for subjects less than 6 years and weight greater or equal to 26kg (0.032 mg/kg/day)

Weight	Dose	Frequency and/or Regimen	Total Daily Dose	Pharmaceutical form and route of administration
26-39.5	2 × 0.5 mg	q.d	1 mg	Tablets for oral administration
39.6-54.5 kg	3 × 0.5 mg	q.d	1.5 mg	Tablets for oral administration
≥ 54.6 kg	1 × 2 mg	q.d	2 mg	Tablets for oral administration

Dose and treatment schedule for trametinib tablets for subjects greater or equal to 6 years and weight greater or equal to 33kg (0.025 mg/kg/day)

Weight	Dose	Frequency and/or Regimen	Total Daily Dose	Pharmaceutical form and route of administration
33-49.5 kg	2 × 0.5 mg	q.d	1 mg	Tablets for oral administration
49.6-69.5 kg	3 × 0.5 mg	q.d	1.5 mg	Tablets for oral administration
≥ 69.6 kg	1 × 2 mg	q.d	2 mg	Tablets for oral administration

Dosing Nomogram – Dabrafenib

1. If a patient's current weight is not a whole number, it should be rounded to its nearest whole number (eg. 12.1 - 12.4 kg is rounded down to 12 and 12.5 – 12.9 is rounded up to 13)
2. Age for daily dose determination in any period during the study is based on the age at enrolment and will remain constant throughout the study.
3. Children < 6 years-old and subjects, regardless of age, with a risk of choking when swallowing capsules will be required to use the dispersible tablet formulation.
4. The investigator or responsible site personnel should instruct the patient and guardians to take or administer the study drug as per protocol (to promote compliance).

Dabrafenib **Capsule** Dosing Nomogram

Dose Level 1 (Starting dose)*					
< 12 year olds			≥ 12 year olds		
Daily dose: 2.63 mg/kg dabrafenib capsule			Daily dose: 2.25 mg/kg dabrafenib capsule		
Body weight (kg)	Capsules/ dose	Total Daily (actual)	Body weight (kg)	Capsules/ dose	Total Daily (actual)
<32	See dispersible tablet for oral suspension nomogram		<38	See dispersible tablet for oral suspension nomogram	
32-47	50 mg	100 mg	38-55	50 mg	100 mg
48-71	75 mg	150 mg	56-83	75 mg	150 mg
72-94	100 mg	200 mg	84-111	100 mg	200 mg
95-118	125 mg	250 mg	112-138	125 mg	250 mg
≥ 119	150 mg	300 mg	≥ 139	150 mg	300 mg

* No dose reduction is allowed for patients on dose level 2.25 or 2.63 mg/kg/day. If a patient requires dose reduction at this level, dabrafenib treatment must be discontinued

Dose Level 2			
< 12 year olds: 5.25 mg/kg dabrafenib capsule			
Dose			Dose Reduction
Body weight (kg)	Capsules/ dose	Total Daily (actual)	Please refer to 4.5 mg/kg dabrafenib capsules dosing nomogram ('Dose' column).
<16	See dispersible tablet for oral suspension nomogram		
16-23	50 mg	100 mg	
24-33	75 mg	150 mg	
34-42	100 mg	200 mg	
43-52	125 mg	250 mg	
≥ 53	150 mg	300 mg	

Dose Level 2			
≥ 12 year olds: 4.5 mg/kg dabrafenib capsule			
Dose			Dose Reduction
Body weight (kg)	Capsules/ dose	Total Daily (actual)	Please refer to 3.75 mg/kg dabrafenib capsules dosing nomogram.
<19	See dispersible tablet for oral suspension nomogram		
19-27	50 mg	100 mg	
28-38	75 mg	150 mg	
39-50	100 mg	200 mg	
51-61	125 mg	250 mg	
≥ 62	150 mg	300 mg	

3.75 mg/kg dabrafenib capsule		
Body weight (kg)	Capsules/ dose	Total Daily (actual)
<26	See dispersible tablet for oral suspension nomogram	
26-33	50 mg	100 mg
34-46	75 mg	150 mg
47-59	100 mg	200 mg
60-73	125 mg	250 mg
≥ 74	150 mg	300 mg

Dabrafenib 10mg Dispersible Tablet for oral (suspension) Dosing Nomogram

Dose and treatment schedule for dabrafenib (DRB436) 10mg dispersible tablets for patients less than 12 years of age (5.25mg/kg/day)

Weight (kg)	Dose	Frequency and/or Regimen	Total Daily Dose	Pharmaceutical form and route of administration
7-9.5	20 mg	b.i.d	40 mg	Dispersible tablet for oral suspension
9.6-13.5	30 mg	b.i.d	60 mg	Dispersible tablet for oral suspension
13.6-17.5	40 mg	b.i.d	80 mg	Dispersible tablet for oral suspension
17.6-20.5	50 mg	b.i.d	100 mg	Dispersible tablet for oral suspension
20.6-24.5	60 mg	b.i.d	120 mg	Dispersible tablet for oral suspension
24.6-28.5	70 mg	b.i.d	140 mg	Dispersible tablet for oral suspension
28.6-32.5	80 mg	b.i.d	160 mg	Dispersible tablet for oral suspension
32.6-36.5	90 mg	b.i.d	180 mg	Dispersible tablet for oral suspension
36.6-40.5	100 mg	b.i.d.	200 mg	Dispersible tablet for oral suspension

40.6-43.5	110 mg	b.i.d	220 mg	Dispersible tablet for oral suspension
43.6-47.5	120 mg	b.i.d	240 mg	Dispersible tablet for oral suspension
47.6-51.5	130 mg	b.i.d	260 mg	Dispersible tablet for oral suspension
51.6-55.5	140 mg	b.i.d.	280 mg	Dispersible tablet for oral suspension
≥55.6 kg	150 mg	b.i.d	300 mg	Dispersible tablet for oral suspension

Dose and treatment schedule for dabrafenib (DRB436) 10mg dispersible tablet for patients greater than or equal 12 years of age (4.5 mg/kg/day)

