All parts of the study will use currently available trametinib tablet strengths (0.5, and 2 mg tablets) for children who are able to reliably swallow tablets. In addition, an oral solution formulation (0.05 mg/mL) is available. Doses will be calculated using body weight in kilograms and prescribed using a dosing nomogram (See Appendix 2).

For Part C and Part D of the study dabrafenib capsules (50, 75 mg) or 10mg dispersible tablet will be used.

General outline of study conduct:

- The screening visit will be completed within 14 days prior to enrollment.
- Safety and PK assessments will be performed at regular intervals as outlined in the Time and Events Tables (Section 7.1).

- Overall response will be assessed at regular intervals as outlined in the Time and Events Tables according to the appropriate guidelines as determined by the disease(s) under study (see Appendix 3 through Appendix 7).
- Additional details for the conduct of each part of the study are provided in Section 3.2 (Part A) Section 3.3 (Part B), Section 3.4 (Part C) and Section 3.5 (Part D).

Protocol waivers or exemptions are not allowed. Therefore, adherence to the study design requirements, including those specified in the Time and Events Table (Section 7.1), are essential.

Two interim analyses (IAs) are planned for decision making of future development options and the data may be used for publication. No decision regarding the conduct of this study will be made at IAs. The first IA will be performed after all subjects in Cohort B3 (NF-1 with PN) have been enrolled and have completed at least three post baseline tumor assessments or have discontinued treatment earlier. The second IA will be performed after all subjects have been enrolled in cohort D1 (LGG) and have completed at least 12 months of treatment or have discontinued treatment earlier. At the time of each IA, the data from other disease cohorts and study parts will also be analyzed. Safety and tolerability will be monitored closely on a continuing basis.

Final analysis will be performed at the time of study completion (see [Section 6.5](#)).

Supplementary study conduct information not mandated to be present in this protocol is provided in the accompanying Study Procedures Manual (SPM). The SPM provides site personnel with administrative and detailed technical information that does not impact subject safety.

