3.15 Guidelines for Dose Modifications and Toxicity Management for Combination Therapy

If treatment related toxicities occur when dabrafenib is used in combination with trametinib then both treatments should be simultaneously dose reduced, interrupted or discontinued with the exception shown below:

- Dose modification is necessary for only dabrafenib
 - Mild to moderate pyrexia ([Section 3.15.1](#))
 - Uveitis ([Section 3.13.5](#) and [Section 3.14](#))
- Dose modifications are necessary for only trametinib:
 - Retinal vein occlusions (RVO) and retinal pigment epithelial detachment (RPED) ([Section 3.13.5](#))
 - Left ventricular ejection fraction (LVEF) reduction (asymptomatic, [Section 3.12.3.1](#))
 - Pneumonitis and interstitial lung disease (ILD) (grade 4, [Section 3.13.7](#))

The severity of adverse events (AEs) will be graded utilizing the NCI-CTCAE v4.03 ([NCI 2009](#)). Guidelines for dose modifications and interruptions for management of common toxicities associated with dabrafenib are provided in this section.

Trametinib dose reduction for patients enrolled in all parts of the study should follow dose reduction column in the trametinib dosing nomogram in Appendix 2.

Dabrafenib dose reduction should follow the dose reduction column in the dabrafenib dosing nomogram in Appendix 2 provided for patients enrolled in Part C and Part D, as described below

- Dabrafenib dose modification levels in Part C
 - If a subject is dosed at Dose Level 1, and requires dose reduction, treatment must be discontinued
 - If a subject is dosed at Dose Level 2, and requires dose reduction, follow the dose reduction column in dosing nomogram
- Dabrafenib dose modification levels in Part D.
 - Follow dose reduction column in dosing nomogram

Nomograms for each dosing level are provided in [Appendix 2](#).

If a second dose reduction is required, the treatment should be discontinued.

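### Two reduced-dose mg cells in the trametinib 0.0125 mg/kg solution nomogram are ten times what the adjacent volume contains: a small correction in binding text, with little practical reach

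*Protocol*

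**What the plan says.** The table concerned is headed "DOSE LEVEL: 0.0125 mg/kg/dose SUBJECT WEIGHT: ≤ 19.4 kg" and "FORMULATION: TRAMETINIB 0.05 MG/ML ORAL SOLUTION". Section 3.1 gives the same strength: "an oral solution formulation (0.05 mg/mL) is available". Each row lists weight band, full dose in mL, full dose in mg, reduced dose in mL and reduced dose in mg.

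The two rows at issue are "4.4-5.2 1.2 0.06 0.9 0.45" and "5.3-6.1 1.4 0.07 1.1 0.55". The rows on either side are "3.7-4.3 1 0.05 0.8 0.04" and "6.2-6.7 1.6 0.08 1.2 0.06".

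The column is operative. Section 3.11.1 makes the Appendix 2 nomogram the means of prescribing trametinib. Section 3.15 says that trametinib reductions in all parts of the study "should follow dose reduction column in the trametinib dosing nomogram in Appendix 2". The mandatory dose-modification tables in Sections 3.12 to 3.15 also send sites to that column.

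**The concern.** A cell in a dose-reduction column should be smaller than the full dose on its row, and a volume and a mass quoted side by side should agree at the stated concentration. On these two rows both conditions fail for the mg cell. A site that writes the reduced dose in mg rather than mL would be working from a figure that contradicts the volume beside it and exceeds the dose being reduced.

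The contradiction also touches Section 4.5, which defines overdose relative to the dose the protocol specifies. On these rows the protocol specifies two incompatible reduced doses, so the definition has no single reference value there.

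**Working it through.** **Inputs**, all from Appendix 2: strength 0.05 mg/mL; 4.4-5.2 kg row, full dose 1.2 mL / 0.06 mg, reduced 0.9 mL / 0.45 mg; 5.3-6.1 kg row, full dose 1.4 mL / 0.07 mg, reduced 1.1 mL / 0.55 mg.

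**Step 1. Does the table's own rule reproduce?** The rule is mg = mL × 0.05.

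- Row above (3.7-4.3 kg): 1 × 0.05 = 0.05 and 0.8 × 0.05 = 0.04. Both match.
- Row below (6.2-6.7 kg): 1.6 × 0.05 = 0.08 and 1.2 × 0.05 = 0.06. Both match.
- Full doses on the two rows at issue: 1.2 × 0.05 = 0.06 and 1.4 × 0.05 = 0.07. Both match.

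**Step 2. The reduced doses on the two rows.**

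| Weight band | Reduced mL | mL × 0.05 | Printed mg | Printed / contained | Printed reduced mg / full mg | Reduced mL / full mL |
|---|---|---|---|---|---|---|
| 4.4-5.2 kg | 0.9 | 0.045 | 0.45 | 10.0 | 0.45/0.06 = 7.5 | 0.9/1.2 = 75% |
| 5.3-6.1 kg | 1.1 | 0.055 | 0.55 | 10.0 | 0.55/0.07 = 7.9 | 1.1/1.4 = 79% |

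The volume ratios of the neighbouring rows are 0.8/1 = 80% and 1.2/1.6 = 75%, so the mL cells of the two rows fit the pattern around them.

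**Step 3. Is the mismatch isolated?** The same rule was applied to the dose and dose-reduction columns of all 61 trametinib solution rows that give both in mL and mg, 22 of them in this table. Only these two cells fail. The 0.032 mg/kg tables are outside the check because they have no reduced-dose cells of their own.

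**Step 4. Internal comparison.** A later solution table in the same appendix has a 2.6-3.5 kg row with the same full dose (1.4 mL, 0.07 mg) and the same reduced volume (1.1 mL) as the 5.3-6.1 kg row. It prints 0.055 mg where the row at issue prints 0.55 mg. The appendix thus gives two masses for one volume of one solution.

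**Step 5. The printed mg in mg/kg.** 0.45/5.2 = 0.087 to 0.45/4.4 = 0.102, and 0.55/6.1 = 0.090 to 0.55/5.3 = 0.104. The table's nominal full dose is 0.0125 mg/kg.

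**Step 6. Who could be on these rows?**

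- 0.0125 mg/kg/day is Dose Level 1 of Part A (Table 3-1).
- Sections 3.1 and 5.2.1.2 keep children under 2 years out of the initial escalation.
- Section 3.2.4 treats the age-expansion cohorts, which include infants from 1 month, at the dose found in the escalation. It lets an age group with excess DLTs continue at a lower level, and it contemplates a review at Dose Level 1. That is the one route to these rows.
- The Amendment 5 rationale declares 0.025 mg/kg/day the recommended dose from 1 month to under 18 years. The Amendment 9 rationale says all cohorts are closed to enrolment.
- Reductions from higher levels do not lead here. The other tables have their own reduction columns, the 0.032 mg/kg tables point to the 0.025 mg/kg table, and Section 3.13 allows only one trametinib reduction.

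**The case against.** The best case on the other side is that this is a typographical slip with almost no consequence, and much of that stands. The product is a liquid drawn up in a graduated syringe (Section 3.11.1), and the volumes on both rows are genuine reductions. To give the printed mg, staff would have to draw 0.45/0.05 = 9 mL against a full dose of 1.2 mL, or 0.55/0.05 = 11 mL against 1.4 mL, and the clash would be visible on the row. Almost nobody could have been on these rows under the design.

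Three stronger readings are tempting, and the protocol does not support them.

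- A reader might divide the printed mg/kg by 0.04 mg/kg/day, the level that exceeded the MTD, obtain 2.2 to 2.6 (0.087/0.04 and 0.104/0.04), and infer that infants were exposed to such a dose. The arithmetic is correct, but nothing shows that any subject was dosed from these rows.
- A reader might call this the working prescribing table for infants of 4.4-6.1 kg. At this dose level infants could enter only by the de-escalation route in Section 3.2.4, and nothing says it was used.
- A reader might infer that exposure or dose-intensity summaries are corrupted. Section 4.4 has sites record what was dispensed and taken, and dose reductions. Nothing says that summaries are built from the nomogram's mg column.

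What the objection does not remove is the contradiction itself, in a column that the current protocol makes binding. A prescription written in mg could still carry it.

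**Conclusion.** The point holds in a limited form. On two rows, the reduced-dose mg cell is exactly ten times the content of the stated volume and 7.5 or 7.9 times the full dose in mg. The discrepancy is confined to those two mg cells: the volumes beside them show a reduction, and the rest of the table is consistent. This is a minor correction with a safety rationale, not a defect that must hold up the study.

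Two assumptions lie behind this. The first is that the cells print in the protocol as they read in its text. Three-decimal cells such as 0.075, 0.085 and 0.105 in the same column keep their digits, so a lost zero in reading is unlikely but not excluded. The second is that a subject of 4.4-6.1 kg would in practice be under 2 years old, which is what makes the reach small.

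**What to change.** Reconcile the mL and mg entries of the 4.4-5.2 kg and 5.3-6.1 kg rows with the stated 0.05 mg/mL strength, and issue the corrected page to sites. The sponsor has to determine and confirm the intended entries; no dose is proposed here. If a record check is wanted, limit it to subjects ever dosed at 0.0125 mg/kg while in these weight bands, which may well be none. The cost is two table cells, one site notice and at most one short data query.
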